7.2.3 UTSW Reporting Requirements

The UTSW IRB requires reporting of all UPIRSOs according to the guidance below. For participating centers other than UTSW, local IRB guidance should be followed for local reporting of serious adverse events. All SAEs occurring during the protocol-specified monitoring period should be submitted to the UTSW study team within 5 business days of the center learning of the event.

7.2.3.1 UPIRSOs occurring on the study require expedited reporting, and are submitted to the UTSW IRB through the UTSW eIRB by the UTSW study team and to the SCCC DSMC Coordinator. Hardcopies or electronic versions of the eIRB report; FDA Form #3500A forms, or other sponsor forms, if applicable; and/or any other supporting documentation available should be submitted to the UTSW study team and will be forwarded to the DSMC Coordinator. The DSMC Coordinator forwards the information onto the DSMC Chairman who determines if immediate action is required. Follow-up eIRB reports, and all subsequent SAE documentation that is available are also submitted to the DSMC Chair who determines if further action is required. (See Appendix IV of the SCCC DSMC Plan for a template Serious Adverse Event Form which may be utilized when a sponsor form is unavailable and SAE submission to the eIRB is not required).

All SAE/UPIRSOs at all sites, which occur in research participants on protocols for which the SCCC is the DSMC of record require reporting to the DSMC regardless of whether IRB reporting is required. All SAEs/UPIRSOs occurring during the protocol-specified monitoring period should be submitted to the SCCC DSMC within 5 business days of the PI or delegated study team members awareness of the event(s). In addition, for participating centers other than UTSW, local IRB guidance should be followed for local reporting of serious adverse events.

The UTSW study team is responsible for submitting SAEs/UPIRSOs to the SCCC DSMC Coordinator. Hardcopies or electronic versions of the eIRB Reportable Event report; FDA

Form #3500A forms, or other sponsor forms, if applicable; and/or any other supporting documentation available should be submitted to the DSMC coordinator. The DSMC Coordinator forwards the information onto the DSMC Chairman who determines if immediate action is required. Follow-up eIRB reports, and all subsequent SAE/UPIRSO documentation that is available are also submitted to the DSMC Chair who determines if further action is required.

If the event occurs on a multi-institutional clinical trial coordinated by the UTSW, Simmons Cancer Center, the DOT Manager or lead coordinator ensures that all participating sites are notified of the event and resulting action, according to FDA guidance for expedited reporting. DSMC Chairperson reviews all SAEs/UPIRSOs upon receipt from the DSMC Coordinator. The DSMC Chairperson determines whether action is required and either takes action immediately, convenes a special DSMC session (physical or electronic), or defers the action until a regularly scheduled DSMC meeting.

Telephone reports to: Investigator: [name] [contact] (business hours) or [contact] (nights and weekends)
 
UTSW SCCC Data Safety Monitoring Committee Coordinator (if fax report is not available) within 5 working days to [contact].

Written reports to: Investigator: [name], Department of Pediatrics - Oncology [name] [contact] (business hours) or [contact] (nights and weekends) [contact]
 
UTSW SCC Data Safety Monitoring Committee Coordinator Email: [contact] [contact] or deliver to [name]
 
UTSW Institutional Review Board (IRB) Submit via eIRB with a copy of the final sponsor report as attached supporting documentation

1. SAEs

Serious adverse events occurring at sites other than UT Southwestern Medical Center will be promptly (less than 2 business days) reported to [contact] and [name]. These adverse events will be evaluated as whether or not they are related to study participation.

Serious adverse events (SAEs) for studies where SCC DSMC is the DSMC of record require reporting to the DSMC coordinator within 5 working days of PI awareness, or as described in the protocol.

2. Unanticipated Problems Involving Risks to Subjects or Others (UPIRSOs)

Local Serious Adverse Event UPIRSOs require reporting to the UTSW IRB within 5 days of PI awareness of the event (life threatening or fatal events experienced by subjects enrolled by the investigator(s) under UTSW IRB jurisdiction).

Local UPIRSOs (non-serious events experienced by subjects enrolled by the investigator(s) under UTSW IRB jurisdiction) require reporting to the UTSW IRB within 5 business days of PI awareness.

External UPIRSOs including those that occur as non-local events, require reporting to the UTSW IRB within 10 working days of PI awareness of the event.

For further guidance for Investigators regarding safety reporting requirements for INDs and BA/BE studies, refer to FDA Draft Guidance document:

<http://www.fda.gov/downloads/Drugs/GuidanceComplianceRegulatoryInformation/Guidances/UCM227351.pdf>

7.3 Steps to Determine If an Adverse Event Requires Expedited Reporting

Step 1: Identify the type of adverse event using the NCI Common Terminology Criteria for Adverse Events (CTCAE v5).

Step 2: Grade the adverse event using the NCI CTCAE v5.

Step 3: Determine whether the adverse event is related to the protocol therapy Attribution categories are as follows:

- Definite – The AE is *clearly related* to the study treatment.
- Probable – The AE is *likely related* to the study treatment.
- Possible – The AE *may be related* to the study treatment.
- Unlikely – The AE *may NOT be related* to the study treatment.
- Unrelated – The AE is *clearly NOT related* to the study treatment.

Note: This includes all events that occur within 30 days of the last dose of protocol treatment. Any event that occurs more than 30 days after the last dose of treatment and is attributed (possibly, probably, or definitely) to the agent(s) must also be reported accordingly.

Step 4: Determine the prior experience of the adverse event.

Expected events are those that have been previously identified as resulting from administration of the treatment. An adverse event is considered unexpected, for expedited reporting purposes only, when either the type of event or the severity of the event is not listed in:

- the current known adverse events listed in the Agent Information Section of this protocol;
- the drug package insert;
- the current Investigator's Brochure
- the study agent's background and associated known toxicities section of this protocol.

7.4 Serious Adverse Events

7.4.1 Definitions

A serious adverse event is an undesirable sign, symptom or medical condition which:

- is fatal or life-threatening

- results in persistent or significant disability/incapacity
- constitutes a congenital anomaly/birth defect
- requires inpatient hospitalization or prolongation of existing hospitalization, unless hospitalization is for:
 - routine treatment or monitoring of the studied indication, not associated with any deterioration in condition.
 - elective or pre-planned treatment for a pre-existing condition that is unrelated to the indication under study and has not worsened since the start of study drug
 - treatment on an emergency outpatient basis for an event not fulfilling any of the definitions of a SAE given above and not resulting in hospital admission
 - social reasons and respite care in the absence of any deterioration in the patient's general condition
- is medically significant, i.e., defined as an event that jeopardizes the patient or may require medical or surgical intervention to prevent one of the outcomes listed above

7.4.2 Reporting Requirements

The principal investigator, [name], has the obligation to report all serious adverse events to the FDA, IRB, and Novartis Pharmaceuticals Drug Safety and Epidemiology Department (DS&E).

All events reported to the FDA by the investigator are to be filed utilizing the Form FDA 3500A (MedWatch Form).

To ensure patient safety, every SAE, regardless of suspected causality, occurring:

- after the patient has provided informed consent and until at least 30 days after the patient has stopped study treatment/participation
- after protocol-specified procedures begin and 30 days after the patient has stopped study treatment
- after the start of any period in which the study protocol interferes with the standard medical treatment given to a patient (e.g., treatment withdrawal during washout period, change in treatment to a fixed dose of concomitant medication) and until 30 days after the patient has stopped study treatment

must be reported to Novartis within 24 hours of learning of its occurrence (**[contact]**) This includes serious, related, labeled (expected) and serious, related, unlabeled (unexpected) adverse experiences. All deaths during treatment or within 30 days following completion of active protocol therapy must be reported within 5 working days.

Any SAEs experienced after this 30 days period should only be reported to Novartis if the investigator suspects a causal relationship to the study drug. Recurrent episodes, complications, or progression of the initial SAE must be reported as follow-up to the original episode within 24 hours of the investigator receiving the follow-up information. A SAE occurring at a different time interval or otherwise considered completely unrelated to a previously reported one should be reported separately as a new event. The end date of the first event must be provided.

The original copy of the SAE Report and the fax confirmation sheet must be kept within the Trial Master File at the study site.

Follow-up information is sent to the same fax number as the original SAE Report Form was sent, using a new fax cover sheet, stating that this is a follow-up to the previously reported SAE, and giving the date of the original report. Each re-occurrence, complication, or progression of

the original event should be reported as a follow-up to that event regardless of when it occurs. The follow-up information should describe whether the event has resolved or continues, if and how it was treated, and whether the patient continued or withdrew from study participation.

If the SAE is not previously documented in the Everolimus Investigator Brochure or Package Insert (new occurrence) and is thought to be related to the Novartis study drug, a DS&E associate may urgently require further information from the investigator for Health Authority reporting. Novartis may need to issue an Investigator Notification (IN), to inform all investigators involved in any study with the same drug that this SAE has been reported. Suspected Unexpected Serious Adverse Reactions (SUSARs) will be collected and reported to the competent authorities and relevant ethics committees in accordance with Directive 2001/20/EC or as per national regulatory requirements in participating countries.

For Comparator Drugs/Secondary Suspects (Concomitant Medications), all serious adverse experiences will be forwarded to the comparator drug company by the investigator.

7.5 Pregnancy

Preclinical data regarding reproductive toxicity is described in the most recent Investigator Brochure. The potential reproductive risk for humans is unknown. Women of childbearing potential should be advised to use highly effective contraception methods while they are receiving everolimus and up to 8 weeks after treatment has been stopped.

To ensure patient safety, each pregnancy occurring while the patient is on study treatment must be reported to Novartis within 24 hours of learning of its occurrence. The pregnancy should be followed up to determine outcome, including spontaneous or voluntary termination, details of the birth, and the presence or absence of any birth defects, congenital abnormalities, or maternal and/or newborn complications. The newborn will be followed for at least 12 months.

Pregnancy should be recorded on a Clinical Trial Pregnancy Form and reported by the investigator to the oncology Novartis Drug Safety and Epidemiology Department (DS&E). Pregnancy follow-up should be recorded on the same form and should include an assessment of the possible relationship to the study treatment and any pregnancy outcome. Any SAE experienced during pregnancy must be reported on the SAE Report Form.

7.6 Stopping Rules

Occurrence of >30% of patients requiring permanent discontinuation of Everolimus in this study (i.e., 4 of the first 10 patients or 6 of the first 16 patients) will lead to stopping this study. A minimum of six patients will be treated.

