Existing data regarding the anti-tumor activity of mTOR inhibitors among children has demonstrated that mTOR inhibitors are well tolerated and have activity against pediatric brain tumors. For example, Franz et al. reported five children with tuberous sclerosis complex and progressive subependymal giant cell astrocytomas who were treated with sirolimus to achieve target trough concentrations between 5 – 15 ng/mL.²³ All tumors demonstrated objective responses to sirolimus. One patient who interrupted sirolimus therapy experienced tumor progression that responded to resumption of sirolimus therapy. A subsequent phase III study of everolimus compared responses of 78 patients treated with everolimus versus 39 patients treated with placebo. 27 of 78 (35%) patients in the everolimus group had at least 50% reduction in the volume of subependymal giant cell astrocytomas versus none in the placebo group ($p<0.0001$). Adverse events were mostly grade 1 or 2 and no patients discontinued treatment because of adverse events.²⁴ A phase I study of everolimus by Fouladi et al. evaluated everolimus at doses between 3 - 6.5 mg/m²/day.²⁵ No children in this study had objective tumor responses, 6 of 18 children who were assessable for response had stable disease for 4 to 14 months. In this study there were 4 children with ependymomas, one who had prolonged stable disease and three other who had progressive disease. Of the 25 children with a variety of different pediatric cancers

enrolled on this study, tumors from 13 of 14 patients demonstrated immunoreactivity against phosphorylated S6 [average of 33%; range = 10% - 90%]. In this study, no relationship was observed between the level of phosphorylated S6 immunoreactivity in pretreatment tumor samples and patients' tumor response.

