4.5 Recommended Dose of Everolimus

The recommended starting dose is 4.5 mg/m²/dose, once daily. Continue treatment for up to 2 years, until disease progression or unacceptable toxicity occurs. After 2 years of therapy, patients will complete the study protocol, but may continue therapy using commercially available drug based upon the clinical judgment of their treating physician and the child's parents or guardians.

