4.8 Duration of Therapy

In the absence of treatment delays due to adverse events, treatment may continue for 2 years or until:

- Disease progression
- Inter-current illness that prevents further administration of treatment
- Unacceptable adverse event(s)
- Patient decides to withdraw from the study, **OR**
- General or specific changes in the patient's condition render the patient unacceptable for further treatment in the judgment of the investigator.

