5.5 Removal of Subjects from Study

Patients can be taken off the study treatment and/or study at any time at their own request, or they may be withdrawn at the discretion of the investigator for safety, behavioral or administrative reasons. The reason(s) for discontinuation will be documented and may include:

- 5.5.1 Patient voluntarily withdraws from treatment (follow-up permitted);
- 5.5.2 Patient withdraws consent (termination of treatment and follow-up);
- 5.5.3 Patient is unable to comply with protocol requirements;
- 5.5.4 Patient demonstrates disease progression (unless continued treatment with study drug is deemed appropriate at the discretion of the investigator);
- 5.5.5 Patient experiences toxicity that makes continuation in the protocol unsafe;
- 5.5.6 Treating physician judges continuation on the study would not be in the patient's best interest;

- 5.5.7 Patient becomes pregnant (pregnancy to be reported along same timelines as a serious adverse event);
- 5.5.8 Development of second malignancy (except for basal cell carcinoma or squamous cell carcinoma of the skin) that requires treatment, which would interfere with this study;
- 5.5.9 Lost to follow-up: If a research subject cannot be located to document survival after a period of 2 years, the subject may be considered "lost to follow-up." All attempts to contact the subject during the two years must be documented and approved by the Data Monitoring Committee.

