9.2 Sample Size and Accrual

Simon's two-stage optimal design³⁵ is used to compute the number of patients to be recruited for this phase II trial. The null hypothesis that the true objective response rate (ORR) is 10% will be tested against a one-sided alternative. In the first stage, 7 patients will be accrued. If there is no ORR seen in these 7 patients, the study will be stopped.

Otherwise, 11 additional patients will be accrued for a total of 18 patients. The null hypothesis will be rejected if 4 or more ORRs are observed in 18 patients. This design yields a type I error rate of 10% and power of 80% when the true ORR is 30%. It is expected that the accrual will be completed in 2 years since 9 patients are expected to be recruited in a year.

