10.5 Data Management and Monitoring / Auditing

REDCap is the UTSW SCC institutional choice for electronic data capture of case report forms for this and all SCC investigator initiated trials. REDCap will be used for electronic data capture case report forms in accordance with Simmons Cancer Center requirements.

Other institutions participating in this trial as sub-sites will be expected to enter data into REDCap and upload de-identified source materials as instructed by the study team to facilitate remote source to case report form verification.

Trial monitoring will be conducted no less than annually and refers to a regular interval review of trial related activity and documentation performed by the DOT, which includes but is not limited to accuracy of case report forms, protocol compliance timelines and accuracy of Velos entries and AE/SAE management and reporting. Documentation of trial monitoring will be maintained along with other protocol related documents and will be reviewed during the internal audit.

The UTSW Simmons Cancer Center (SCC) Data Safety Monitoring Committee (DSMC) is responsible for monitoring data quality and patient safety for all UTSW SCC clinical trials. As part of that responsibility, the DSMC reviews all local serious adverse events and unanticipated problems in real time as they are reported and reviews adverse events on a quarterly basis. The quality assurance activity for Clinical Research Office provides periodic auditing of clinical research documents to insure data integrity and regulatory compliance. A copy of the DSMC plan is available upon request.

The SCC DSMC meets quarterly and conducts annual comprehensive reviews of ongoing clinical trials, for which it serves as the DSMC of record. The QAC works as part of the DSMC to conduct regular audits based on the level of risk. Audit findings are reviewed at the next available DSMC meeting. In this way frequency of DSMC monitoring is dependent

upon the level of risk. Risk level is determined by the DSMC Chairman and a number of factors such as the phase of the study, the type of investigational agent, device or intervention being studied, and monitoring required to ensure the safety of study subjects based on the associated risks of the study. Protocol specific DSMC plans must be consistent with these principles.

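### The stopping rule in Section 7.6 contradicts itself at 5 of 16: that is 31.25%, above the stated 30% limit, but the written count is 6

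*Combined protocol and SAP*

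**What the plan says.** Section 7.6 (Stopping Rules), within Section 7 (Adverse Events), makes stopping mandatory on ">30% of patients requiring permanent discontinuation of Everolimus in this study (i.e., 4 of the first 10 patients or 6 of the first 16" patients, and adds: "A minimum of six patients will be treated". The counts in brackets are introduced as a restatement of the percentage, not as a separate rule.

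No cause of discontinuation is named in 7.6. Elsewhere the drug is stopped for more than toxicity. Section 4.5 reads "Continue treatment for up to 2 years, until disease progression or unacceptable toxicity occurs", Section 4.8 lists progression among the reasons for ending treatment, and so does Section 5.5.4: "Patient demonstrates disease progression (unless continued treatment with study drug is deemed appropriate at the discretion of the investigator".

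Section 9.2 sets the size of the trial at 7 patients in stage 1 and then: "Otherwise, 11 additional patients will be accrued for a total of 18 patients".

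**The concern.** A percentage and a count presented as the same threshold should give the same decision on the same data. If five of the first 16 patients have permanently stopped everolimus, one committee member can apply the percentage and stop the study. Another can apply the count and continue. Both would be following the text.

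The rule is mandatory, the trial is in children, and whether treatment on protocol goes on would depend on which half of one sentence is read. The rule bears on safety monitoring only. It plays no part in the test of the response rate.

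**Working it through.** **Inputs.** From Section 7.6: a limit strictly above 30%, and counts of 4 of the first 10 and 6 of the first 16. The discontinuation rate q is assumed, because the documents give none for this population.

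**Step 1: do the counts match the percentage?** The matching count at n patients is the smallest r with r/n > 0.30.

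| Patients | One fewer | Smallest count above 30% | Written count | Agree? |
|---|---|---|---|---|
| 10 | 3/10 = 30.0% (not above) | 4/10 = 40.0% | 4 | yes |
| 16 | 4/16 = 25.0% | 5/16 = 31.25% | 6 (37.5%) | no |

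The first count reproduces and the second does not.

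**Step 2: does another reading of the limit rescue it?**
- At least 30%: the counts become 3 of 10 and 5 of 16, so neither written count fits.
- A limit that yields 6 of 16 must be at least 31.25% (so that 5 does not exceed it) and below 37.5%. More than one third lies in that range. It also keeps 4 of 10, since 30.0% is below 33.3% and 40.0% is above.

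**Step 3: how likely is the contradictory result?** Let X be the number of discontinuations in the first 10 patients and Y the number in the next 6, independent binomials with rate q. The two halves of the rule conflict when X is at most 3 and X + Y = 5:

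P(conflict) = Σ over x = 0 to 3 of P(X = x) · P(Y = 5 − x).

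At q = 0.10 the four terms are 0.00002, 0.00047, 0.00282 and 0.00565, which sum to 0.0090. At q = 0.20 they are 0.00016, 0.00412, 0.02474 and 0.04948, which sum to 0.0785.

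**Step 4: what does each version of the rule do?** With second count c,

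P(stop) = P(X ≥ 4) + Σ over x = 0 to 3 of P(X = x) · P(Y ≥ c − x).

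| Assumed q | P(X ≥ 4) | P(stop), c = 6 (as written) | P(stop), c = 5 | Difference = P(conflict) |
|---|---|---|---|---|
| 5% | 0.0010 | 0.0011 | 0.0016 | 0.0005 |
| 10% | 0.0128 | 0.0140 | 0.0229 | 0.0090 |
| 20% | 0.1209 | 0.1463 | 0.2248 | 0.0785 |
| 30% | 0.3504 | 0.4364 | 0.5736 | 0.1372 |

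The last column equals the result of Step 3, as it must: the two versions differ only when exactly 5 of 16 is reached without an earlier stop. (At 10% the rounded entries differ by 0.0089; unrounded, the difference is 0.00896.) These are chances that a boundary is ever met. They do not say when.

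**The case against.** The best defence is that the counts are the working rule and the percentage is only a gloss. A committee that follows the counts has clear instructions at 10 and at 16, and the conflict is confined to one outcome that is improbable at low rates. In addition, "the DSMC reviews all local serious adverse events and unanticipated problems in real time as they are reported" (Section 10.5), so a serious safety signal would not wait for this boundary. All of that supports a low severity. It does not make the sentence consistent, and real-time review does not tell the committee which threshold governs.

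Three stronger or broader readings are tempting and should not be drawn.

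- **The percentage applies after every patient from the sixth.** A reader might infer this from the six-patient minimum and then find further conflicts at small numbers. The text does not support it. The bracketed counts name 10 and 16 as the operative numbers. The minimum also has a complete purpose without continuous checking: four discontinuations could occur among the first four or five patients, and it prevents a stop before six are treated.
- **Discontinuation for progression counts.** Section 7.6 does not exclude it in words. But the rule sits under Adverse Events, and its wording matches the toxicity tables in Sections 4.5.1 to 4.5.11, which say when the drug must be given up. Lack of activity has its own rule in Section 9.2 (stop after no responses in 7). Counting progression would also defeat the design, which assumes a response rate of 10% under the null and only 30% under the alternative. At assumed all-cause rates of 50% to 70%, the written counts would stop the trial with probability 0.921 to 0.999. The missing cause is a wording gap, not a second error.
- **The conflict comes too late to matter, because 16 of 18 patients are already enrolled.** The documents do not support that either. Sections 4.11 and 6.1.9 allow replacement, so more than 18 may enrol. Treatment can last 2 years, so the fifth discontinuation among the first 16 may fall after accrual has closed, while patients are still on drug.

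**Conclusion.** The point holds and is minor. The stated limit and the second count in Section 7.6 disagree at exactly 5 of 16. That part is plain arithmetic and rests on no assumption.

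The size does rest on assumptions: a constant, independent discontinuation rate, and the two named patient numbers as the only looks. On that basis the conflicting result has probability 0.009 at a 10% rate, 0.079 at 20% and 0.137 at 30%. The nearest figure in the documents is the report in Section 1.3 that, in a phase III trial in subependymal giant cell astrocytoma, "Adverse events were mostly grade 1 or 2 and no patients discontinued treatment because of adverse events". That is a different disease, so it does not fix the rate here.

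The primary analysis and the Simon boundaries in Section 9.2 are unaffected.

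**What to change.** Amend the one paragraph in Section 7.6.

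1. **Preferred:** keep the 30% limit and change the second count from 6 to 5 of the first 16. Both counts then follow from the stated percentage. The cost is a somewhat higher chance of stopping: from 0.014 to 0.023 at an assumed 10% rate, 0.146 to 0.225 at 20%, and 0.436 to 0.574 at 30%.
2. **If 6 of 16 was intended:** keep both counts and restate the limit as more than one third. The chance of stopping stays as the written counts give it, but the declared limit rises from 30% to 33.3%. The sponsor and the monitoring committee should say which was meant.
3. **Wording note:** specify that the discontinuations counted are those due to toxicity, as the placement in Section 7 already implies. Do not narrow this to events attributed to everolimus. Section 7.6 contains no attribution test, and adding one could remove discontinuations of uncertain cause from a safety rule.

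No patients, visits or procedures are added.
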